**Table 6. Anticipated Sample Sizes that May be Observed**

	Treatment Regimen	Potential Subsample*	Potential Subsample*	Combined
Genotype 1	Harvoni® (H)	480	480	960
	Zepatier® (Z)	80	80	160
	VPK®	40	40	80
Genotype 2 & 3	Daclatasvir/sofosbuvir	40	40	80
	**Sofosbuvir/velpatasvir	60	60	120
	Combined	800	800	1600

Note: \* Potential subsamples within treatment regimens may include patients with and without cirrhosis or patients with and without a mental health or substance abuse history. \*\* SOF/VEL is pan-genotypic and may also be used with Geno 1. Anticipated FDA-approval June 28, 2016. \*\*\*Participants with rare genotypes (4, 5, 6) are expected to represent <3% of the sample and will be analyzed based on prescribed treatment regimen, not genotype.

The primary objective of the study will focus on characterizing each treatment regimen or a subgroup of interest. For this purpose, point and interval estimates of mean changes from baseline for the PRO variables of interest will be estimated as a function of subgroups defined by cirrhosis status and other characteristics.

Auxiliary analyses to conduct head to head comparisons of treatment regimens is not the purpose of this study; however, we will take the opportunity to examine similarities and differences between regimens using causal inference methods.

Population inferences will rely on point and interval estimates, and secondarily on two kinds of tests: a 2-sided superiority test of the null hypothesis  $H_0$ : “the difference is exactly zero”, and an equivalence test of the null hypothesis  $H_0$ : “the magnitude of the difference exceeds a threshold that defined ‘equivalence’.”

Equivalence tests will be used for those analyses in which there is an *a priori* belief that equivalence is plausible; for example, in manuscript #2, it is conjectured that the subgroups of interest (patients with and without mental health/substance abuse histories) may be equivalent in regard to medication adherence.

The proposed primary hypothesis tests regarding subgroup differences or temporal changes in mean levels of outcomes will be cirrhosis-subgroup-specific; consequently, the effective sample size available to each test is approximately 800 subjects. For purposes of analysis of the anticipated levels of precision of estimators and the anticipated levels of power of test procedures, we assumed balance of covariates, inclusion of baseline score in models for change from baseline, and that the tests are those of size  $\alpha = 0.05$ .

#### Anticipated levels of precision for interval-scale estimates used to characterize change in PROs.

The appendix provides manuscript-specific details regarding the performance characteristics of the estimators and tests of interest.

- For MSAS estimators of mean change ( $\Delta$ ) from baseline, a change of  $\Delta=0.10$  points is considered clinically important to patients. The half-widths of the confidence intervals for mean change are highly likely (80% chance) to be  $< 0.14$  for  $N=80$ ,  $< 0.10$  for  $N=160$ , and  $< 0.04$  for  $N=960$ . (Appendix Figure 1-1 to Figure 1-6).
- For PROMIS estimators of mean change ( $\Delta$ ) from baseline, a change of  $\Delta=3$  points is considered clinically important. The half-widths of the confidence intervals for mean change are highly likely (80% chance) to be  $< 2.37$  for  $N=80$ ,  $< 1.63$  for  $N=160$ , and  $< 0.65$  for  $N=960$ . (Appendix Figure 2-1 to Figure 2-6).
- For HCV-PRO estimators of mean change ( $\Delta$ ) from baseline, a change of  $\Delta=10$  points is considered clinically important. The half-widths of the confidence intervals for mean change are highly likely (80% chance) to be  $< 6.14$  for  $N=80$ ,  $< 4.23$  for  $N=160$ , and  $< 1.67$  for  $N=960$ . (Appendix Figure 3-1 to Figure 3-6).

#### Anticipated levels of precision for estimates of adherence rates

For estimators of the rate of successful adherence to treatment protocol, population rates that differ by  $<0.05$  will be considered equivalent. The half-widths of the confidence intervals for mean change are highly likely (90% chance) to be  $<0.09$  for  $N=80$ ,  $<0.06$  for  $N=160$ , and  $< 0.03$  for  $N=960$ . (Appendix Figure 4-1 to Figure 4-6).

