#### **15.6 Overview of Plans for Manuscript #2: Medication Adherence during T1 to T2/T3**

Aim 2, Medication Adherence. The analyses concerning adherence will be based on the patient-reported Voils' Medication Adherence Survey (VMAS) at 3 months post-treatment.

Aim 2a. In the combined convenience sample of 1600 participants, two subgroups defined by mental health or substance abuse history (MH/SU Hx: yes, no) will be characterized and compared in terms of medication adherence using the VMAS. We anticipate 50% (n=800) of participants having a MH/SU Hx and 50% (n=800) without a MU/SU Hx. We hypothesize that the two subpopulations are equivalent with regard to medication adherence (<5% difference in medication adherence). Each participant's level of adherence will be classified as high (100% adherent) or low (<100% adherent) for purposes of the analysis. Overall, we anticipate that about 75% of participants will report perfect 100% adherence. Individual adherence may vary depending on treatment regimen, pill burden and patient characteristics. The adherence literature suggests that adherence decreases as the number of pills in the regimen increases (Claxton). The primary characterization of each subgroup, and their comparison, we rely on a logistic regression model for adherence conditional on *subgroup, pill burden, cirrhosis status, age, race, and sex at birth*. The analysis will focus on point estimates and confidence intervals. In particular, the rate (P) of high adherence for each subgroup, and the magnitude of difference between those two rates, are of greatest interest. Of less interest, an equivalence test procedure will be used to test the null hypothesis that the subpopulations do not have equivalent rates. 'Equivalent' will be defined to mean that the difference between population rates, ( $P_1 - P_2$ ), is less than 5%, and thus the null hypothesis is  $|P_1 - P_2| > 5\%$ . For purposes of generating new hypotheses, variations on the model will be explored using additional or alternative covariates such as *marital status, educational status, income level, living situation, employment status, health coverage*, and selected two-way interactions thereof.

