### Anticipated precision of rates and proportions, in general

The figure below illustrates precision for rates and proportions corresponding to binary outcomes indicating, for example, presence or change of a side-effect, perfect medication adherence, and resolution of a symptom. The analyses will provide statistical estimates of the population proportion ( $P$ ). The anticipated level of precision for the estimated proportion can be obtained from the figure. For example, hypothetically if  $N=100$  and  $P=0.50$  is the observed rate of perfect compliance for a treatment regimen, then half the width of a symmetric 95% confidence interval is  $W = 0.10$  and thus the approximate 95% confidence interval would be  $0.50 \pm 0.10$  or “[0.40, 0.60]. Larger sample sizes yield narrower confidence intervals.

Sample Size (N)

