**PRO\_measure = HCV-PRO with Conjectures = { SD = 25.92 [23.641, 28.835] and serial correlation is R = 0.50 }**

**a difference of 10 points on the HCV-PRO scale will be considered clinically important**

Figure	MS	Groups	N	procedure	X_80	X_90
3-1	1, 3, 4	1	1500	Confidence interval [1]	1.34 [1.24,1.50]	1.35 [1.26,1.51]
3-2	1, 3, 4	1	960	Confidence interval [1]	1.67 [1.54,1.88]	1.71 [1.57,1.90]
3-3	1, 3, 4	1	160	Confidence interval [1]	4.23 [3.86,4.71]	4.34 [3.96,4.83]
3-4	1, 3, 4	1	120	Confidence interval [1]	4.94 [4.50,5.49]	5.07 [4.63,5.64]
3-5	1, 3, 4	1	100	Confidence interval [1]	5.44 [4.96,6.05]	5.61 [5.11,6.24]
3-6	1, 3, 4	1	80	Confidence interval [1]	6.14 [5.60,6.83]	6.35 [5.79,7.06]
3-7	1, 3, 4	1	1500	test Ho: 'mean change is zero' [2]	1.88 [1.71,2.09]	2.17 [1.98,2.42]
3-8	1, 3, 4	1	960	test Ho: 'mean change is zero' [2]	2.35 [2.14,2.61]	2.71 [2.48,3.02]
3-9	1, 3, 4	1	160	test Ho: 'mean change is zero' [2]	5.78 [5.27,6.42]	6.68 [6.10,7.43]
3-10	1, 3, 4	1	120	test Ho: 'mean change is zero' [2]	6.68 [6.10,7.43]	7.73 [7.05,8.60]
3-11	1, 3, 4	1	100	test Ho: 'mean change is zero' [2]	7.33 [6.69,8.16]	8.48 [7.74,9.44]
3-12	1, 3, 4	1	80	test Ho: 'mean change is zero' [2]	8.22 [7.50,9.14]	9.51 [8.67,10.58]
3-13	1, 3A, 4	2	800 + 800	test Ho: 'mean diff. is zero' [3]	3.63 [3.31,4.04]	4.20 [3.83,4.68]
3-14	1, 3A, 4	2	1500 + 100	test Ho: 'mean diff. is zero' [3]	7.56 [6.90,8.41]	8.75 [7.98,9.74]
3-15	1, 3A, 4	2	400 + 400	test Ho: 'mean diff. is zero' [3]	5.14 [4.69,5.72]	5.95 [5.43,6.62]
3-16	1, 3A, 4	2	160 + 120	test Ho: 'mean diff. is zero' [3]	8.80 [8.03,9.79]	10.19 [9.29,11.33]
3-17	1, 3A, 4	2	160 + 80	test Ho: 'mean diff. is zero' [3]	10.00 [9.12,11.13]	11.58 [10.56,12.88]
3-18	1, 3A, 4	2	80 + 80	test Ho: 'mean diff. is zero' [3]	11.55 [10.54,12.85]	13.37 [12.19,14.87]
3-19	1, 3A, 4	2	960 + 80	test Ho: 'mean diff. is zero' [3]	8.54 [7.79,9.50]	9.88 [9.01,10.99]
3-20	1, 3A, 4	2	960 + 160	test Ho: 'mean diff. is zero' [3]	6.23 [5.68,6.93]	7.21 [6.57,8.02]

[1]  $\Pr[\text{Confidence Interval's half-width will be } < X_{80}] = 0.80$

[2]  $\Pr[p < \alpha | \text{population mean change} = X_{80}] = 0.80$

[3]  $\Pr[p < \alpha | \text{population mean difference} = X_{80}] = 0.80$

[4]  $\Pr[p < \alpha | \text{population rate change} = X_{80}] = 0.80$

[5]  $\Pr[p < \alpha | \text{population rate difference} = X_{80}] = 0.80$

PRO\_measure = ADHERENCE

with Conjectures = { rate P1 = 0.80 [0.60, 0.90] }

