population rates that differ by less than 0.05 will be considered equivalent

Figure	MS	Groups	N	procedure	X_80	X_90
4-1	1, 2	1	1500	Confidence interval [1]	0.02 [0.03,0.02]	0.02 [0.03,0.02]
4-2	1, 2	1	960	Confidence interval [1]	0.03 [0.03,0.02]	0.03 [0.03,0.02]
4-3	1, 2	1	160	Confidence interval [1]	0.06 [0.08,0.05]	0.07 [0.08,0.05]
4-4	1, 2	1	120	Confidence interval [1]	0.07 [0.09,0.06]	0.08 [0.09,0.06]
4-5	1, 2	1	100	Confidence interval [1]	0.08 [0.10,0.07]	0.08 [0.10,0.07]
4-6	1, 2	1	80	Confidence interval [1]	0.09 [0.11,0.07]	0.09 [0.11,0.08]
4-7	1, 2, 3A	2	800 + 800	test Ho: 'rate difference is zero' [5]	0.06 [0.07,0.05]	0.07 [0.08,0.05]
4-8	1, 2, 3A	2	800 + 800	test Ho: 'rates are equivalent(0.05)' [5]	0.00 [0.00,0.00]	0.00 [0.00,0.00]

[1] Pr[ Confidence Interval's half-width will be < X\_80 ] = 0.80

[2] Pr[ p < alpha | population mean change = X\_80 ] = 0.80

[3] Pr[ p < alpha | population mean difference = X\_80 ] = 0.80

[4] Pr[ p < alpha | population rate change = X\_80 ] = 0.80

[5] Pr[ p < alpha | population rate difference = X\_80 ] = 0.80

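### Section 15.12 gives a 90% chance to adherence half-widths that are the appendix's 80% values; at N=160 the 90% value is 0.07, not 0.06

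*Combined protocol and SAP*

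**What the plan says.** In section 15.12, the paragraph on precision for adherence rates says the half-widths "are highly likely (90% chance) to be" below 0.09 for N=80, 0.06 for N=160 and 0.03 for N=960. It cites Appendix Figures 4-1 to 4-6. It describes the intervals as being for mean change, although the quantity is a rate.

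The appendix adherence table summarises those figures. Its assumption is "rate P1 = 0.80 [0.60, 0.90" (central value, then range). Its footnote 1 defines X_80 as the value for which the chance that the "Confidence Interval's half-width will be" smaller equals 0.80; X_90 is read in the same way with 0.90. In row 4-3 (N=160), X_80 is 0.06 and the X_90 cell begins "0.07 [0.08,0.05".

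The three parallel statements in section 15.12 for MSAS, PROMIS and HCV-PRO attach an 80% chance to X_80 values. For rates, the section's general illustration says "half the width of a symmetric 95% confidence interval is" 0.10 at N=100 and P=0.50, which fixes the confidence level at 95%. Section 15.6 works from a lower adherence rate than the appendix: "we anticipate that about 75% of participants will report perfect 100% adherence".

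**The concern.** The label in the text and the column it draws on do not match. The paragraph claims 90% assurance but prints 80% values, and at N=160 the two columns differ in the second decimal. Section 15.12 says that inference will rest mainly on point and interval estimates, with tests secondary, so these precision statements form part of the case for the sample size. Cohorts of 80 and 160 are the sizes anticipated for the smaller regimens in Table 6. A reader who relies on the text alone would credit the N=160 cohort with slightly more assured precision than the appendix supports.

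**Working it through.** **Inputs.** Bounds 0.09, 0.06 and 0.03 with a 90% label (section 15.12); assumed rate P=0.80 (appendix adherence table); two-sided 95% interval (section 15.12, general illustration), so z=1.96; alternative rate 0.75 (section 15.6). The documents do not name the interval method, so two common ones were used.

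**Step 1. Text against appendix.**

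| N | Section 15.12 (labelled 90%) | Appendix X_80 | Appendix X_90 |
|---|---|---|---|
| 80 | 0.09 | 0.09 | 0.09 |
| 160 | 0.06 | 0.06 | 0.07 |
| 960 | 0.03 | 0.03 | 0.03 |

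All three text values equal X_80. Only N=160 departs from X_90.

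**Step 2. Formulas.** X is binomial(N, P) and p = X/N.

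- Wald half-width: z·√(p(1−p)/N).
- Wilson half-width: [z/(1+z²/N)]·√(p(1−p)/N + z²/(4N²)).

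The chance of meeting a bound is the sum of the binomial probabilities of all X whose half-width lies below it.

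**Step 3. Reproduce the appendix.** Percentiles of the half-width at P=0.80:

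| N | Wilson 80th / 90th | Wald 80th / 90th | Printed X_80 / X_90 |
|---|---|---|---|
| 80 | 0.0919 / 0.0948 | 0.0933 / 0.0964 | 0.09 / 0.09 |
| 160 | 0.0643 / 0.0660 | 0.0647 / 0.0665 | 0.06 / 0.07 |
| 960 | 0.0258 / 0.0260 | 0.0258 / 0.0261 | 0.03 / 0.03 |

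Over rows 4-1 to 4-6, Wilson reproduces all 12 central entries after rounding. Wald reproduces 10; its misses are row 4-4 X_80 (0.0757 against a printed 0.07) and row 4-6 X_90 (0.0964 against a printed 0.09). The appendix is therefore internally sound, and its N=160 entries are right under both methods.

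**Step 4. Chance of meeting the N=160 bound, with 0.06 read as rounded (below 0.065).**

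- Wald: the half-width is 0.0647 at X=124 and 0.0653 at X=123, so X≥124 is needed. P(X≥124) = 0.814.
- Wilson: the half-width is 0.0649 at X=123 and 0.0655 at X=122, so X≥123 is needed. P(X≥123) = 0.861.

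Both are short of 0.90. The same reading at N=80 (below 0.095) gives 0.893 (Wald) and 0.934 (Wilson), in line with the label. At N=960 the chance is 1.000.

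**Step 5. The rate in section 15.6.** At P=0.75 the Wilson 90th percentiles are 0.0996 (N=80), 0.0699 (N=160) and 0.0280 (N=960). The chance of a half-width below 0.065 at N=160 falls to 0.264 (Wald) or 0.328 (Wilson). At P=0.90, the upper end of the appendix range, the N=80 and N=160 bounds are both met with more than 99% chance.

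**The case against.** The best defence is that this is a rounding matter in an illustrative paragraph. Two of the three figures agree with the appendix's 90% column, the third differs by 0.01, and the correct value is printed in the table to which the text points. The appendix also shows how precision varies over rates from 0.60 to 0.90, so the effect of a rate below 0.80 is disclosed. All of that stands, and it limits the importance of the point. It does not remove the mismatch at N=160, which survives the rounded reading under both interval methods.

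Two stronger readings are tempting, and the documents support neither.

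- A reader might take the bounds as exact and infer that the real chance is only 32% at N=160 (the half-width at p=0.80 is 1.96·√(0.8·0.2/160) = 0.062, already above 0.06) and 67% at N=80. Those percentages are correct for exact bounds, but the bounds are printed to two decimals. On that reading the appendix's own X_80 of 0.06 would also be a 32% value, although the table defines it as 80%. The figures mostly measure rounding.
- A reader might infer that row 4-6 (N=80) should show X_90 = 0.10. That follows only from Wald (0.0964), the method that fits the table less well. Wilson gives 0.0948, which rounds to the printed 0.09.

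**Conclusion.** The point holds as a labelling error with a numerical consequence at one sample size. At N=160 the 90%-assurance half-width is about 0.066, printed as 0.07 in the appendix, and the 0.06 in the text carries about 81% to 86% assurance. The N=80 and N=960 figures agree with the appendix after rounding and need no correction. The likely cause is that X_80 values were copied under a 90% label, but the documents do not say so.

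The conclusion rests on P=0.80, a 95% two-sided interval, exact binomial sampling, and reading 0.06 as a two-decimal value. It depends on the rate: the shortfall grows at 0.75 and vanishes at 0.90. The practical effect is about 0.01 in one half-width. Section 15.12 bases N=1600 on several considerations and does not derive it from this figure, and the adherence equivalence test concerns 800 per group, so no test is affected. This is a minor correction.

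**What to change.** In the adherence precision paragraph of section 15.12, do one of the following:

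- change the label to an 80% chance, which matches the three parallel PRO statements and leaves every number as it is; or
- keep 90% and print 0.07 at N=160.

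Preferably, give the values to three decimals as rounded percentiles and name the interval method. With Wilson intervals and 90% chance, these are 0.095, 0.066 and 0.026 for N=80, 160 and 960 at P=0.80. Add the values at the 75% rate of section 15.6: about 0.100, 0.070 and 0.028. In the same sentence, replace the reference to mean change with adherence rate. Leave appendix row 4-6 unchanged; printing 0.10 at N=80 for P=0.80 would create a new conflict between text and table.

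The cost is an edit to one paragraph. No table cell, sample size, test or data collection changes.

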#### Anticipated levels of power of tests for interval scale variables to examine group differences. The appendix provides manuscript-specific details regarding the performance characteristics of the estimators and tests of interest.

- MSAS: The anticipated power level of a test of ‘no difference’ ( $\Delta=0$ ) between two subgroups each of size  $N=80$  is 80% if  $\Delta=0.27$ . For two subgroups of size  $N=800$ , anticipated power is 80% if  $\Delta=0.08$ . (Appendix Figure 1-13 to Figure 1-20). The difference,  $\Delta$ , is considered clinically important if  $\Delta \geq 0.10$ .
- PROMIS: The anticipated power level of a test of ‘no difference’ ( $\Delta=0$ ) between two subgroups each of size  $N=80$  is 80% if  $\Delta=4.46$ . For two subgroups of size  $N=800$ , anticipated power is 80% if  $\Delta=1.40$ . (Appendix Figure 2-13 to Figure 2-20). The difference,  $\Delta$ , is considered clinically important if  $\Delta \geq 3$ .
- HCV-PRO: The anticipated power level of a test of ‘no difference’ ( $\Delta=0$ ) between two subgroups each of size  $N=80$  is 80% if  $\Delta=11.55$ . For two subgroups of size  $N=800$ , anticipated power is 80% if  $\Delta=3.63$ . (Appendix Figure 3-13 to Figure 3-20). The difference,  $\Delta$ , is considered clinically important if  $\Delta \geq 10$ .

[figure not shown]
#### Anticipated level of power of equivalence tests for adherence rates

The anticipated power level of a test of equality between two subgroups each of size  $N=800$  is  $>90\%$  if the subgroup difference is  $\Delta=0.0$ . If the magnitude of difference between subgroups is larger than 0.0, then the power level is smaller.

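### The >90% power stated in 15.12 for the adherence equivalence test is about 49% to 61% at the plan's own expected adherence rates

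*Combined protocol and SAP*

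**What the plan says.** Section 15.12, under the heading on equivalence tests for adherence rates, states: "The anticipated power level of a test of equality between two subgroups each of size $N=800$ is $>90\%$ if the subgroup difference is" 0.0. It adds that power falls if the true difference is larger. No adherence rate is given there.

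The rates appear elsewhere, and there are two:

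- Section 15.6, Aim 2a: "Overall, we anticipate that about 75% of participants will report perfect 100% adherence". Aim 2c is consistent with this, putting imperfect adherers at about 400 of 1600.
- Appendix 2, ADHERENCE: "rate P1 = 0.80 [0.60, 0.90", that is, a central value of 0.80 with a range of 0.60 to 0.90.

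Section 15.6 defines equivalence as a difference in rates below 5 percentage points and makes non-equivalence the null: "Of less interest, an equivalence test procedure will be used to test the null hypothesis that the subpopulations do not have equivalent rates". Section 15.12 sets the size for all power work, assuming "that the tests are those of size" 0.05. The Appendix 2 row for Figure 4-8, labelled "test Ho: 'rates are equivalent(0.05)' [5", prints 0.00 for both 80% and 90% power at all three rates.

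On timing, 15.6 says the adherence analyses "will be based on the patient-reported Voils' Medication Adherence Survey (VMAS) at 3 months post-treatment". Its own heading refers to T2/T3, and Table 4 in 11.4 schedules the VMAS only at T2 and T3.

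**The concern.** The standard error of a difference between two proportions depends on the underlying rate. A power figure for a fixed 5-point margin therefore means little until a rate is named. At rates near 0.75 to 0.80 with 800 per group, that standard error is about 0.02, so the margin is only about 2.3 to 2.5 standard errors. That is too narrow for an equivalence test to succeed more than 90% of the time.

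Equivalence is the hypothesis stated for Aim 2a, and 15.12 uses this comparison as its example of where equivalence testing is appropriate. If the test fails, a reader who trusts >90% power would take the failure as evidence that patients with a mental health or substance use history adhere differently. At 49% to 61% power, failure is nearly as likely as success even when the two groups are identical.

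**Working it through.** **Inputs, all from the plan**

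- n = 800 per subgroup (15.6, 15.12, Appendix 2)
- margin 0.05 (15.6, 15.12, Appendix 2)
- size 0.05 (15.12), applied to each of two one-sided tests, with non-equivalence as the null (15.6)
- true difference 0 (15.12)
- adherence rate P: 0.75 (15.6); 0.80, range 0.60 to 0.90 (Appendix 2)

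**Calibration on the neighbouring row.** Row 4-7 (test of zero difference, 800 + 800) can be reproduced. With the usual two-sided 0.05 test of two proportions and the second rate below the first, the difference giving 80% power is 0.059 [0.069, 0.046], against the printed 0.06 [0.07, 0.05]. For 90% power it is 0.069 [0.080, 0.054], against 0.07 [0.08, 0.05]. The appendix inputs are therefore being read as the authors used them.

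**The equivalence test.** At zero difference:

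SE = sqrt(2P(1 − P)/800)

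Power = 2Φ(0.05/SE − 1.645) − 1

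| P | SE | 0.05/SE − 1.645 | Power | Exact binomial |
|---|---|---|---|---|
| 0.60 | 0.0245 | 0.396 | 30.8% | 30.2% |
| 0.75 | 0.0217 | 0.665 | 49.4% | 49.5% |
| 0.80 | 0.0200 | 0.855 | 60.7% | 60.9% |
| 0.90 | 0.0150 | 1.688 | 90.9% | 90.8% |

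Solving for P, power reaches 80% at about 0.865 and 90% at about 0.897. The stated >90% is reproduced only at the top end of the appendix range.

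**Other readings of the test.** With 800 per group, none exceeds 90% at either expected rate:

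| Test | P = 0.75 | P = 0.80 |
|---|---|---|
| Two one-sided tests, 0.025 each | 27% | 41% |
| Two one-sided tests, 0.10 each | 70% | 78% |
| Single one-sided test, 0.05 | 75% | 80% |
| Single one-sided test, 0.10 | 85% | 89% |

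**Row 4-8.** Power is highest at zero difference. At P = 0.60 and 0.80 that maximum is 31% and 61%, so no difference gives 80% or 90% power and 0.00 cannot be right. At P = 0.90, the difference giving 80% power is 0.011 to 0.014, depending on which side the second rate lies, so that entry should be 0.01. The difference giving 90% power is 0.003 to 0.005, which rounds to the printed 0.00.

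**A small true difference.** A 2-point difference, which the plan itself counts as equivalent, gives 22%, 34%, 41% and 64% power at average rates of 0.60, 0.75, 0.80 and 0.90.

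**Scale only.** For 90% power at zero difference, n per group = 2P(1 − P)(1.645 + 1.645)²/0.05². This is 1,624 at P = 0.75 and 1,386 at P = 0.80.

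**Outcome definition.** If the 75% applies to each survey and a patient must be fully adherent at both T2 and T3, the combined rate lies between 0.75 + 0.75 − 1 = 0.50 and 0.75. Power would then be about 28% to 49%. This is an assumption, because the plan gives no rule for combining the two surveys.

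**The case against.** The strongest reply is that the sentence in 15.12 is incomplete rather than false. It names no rate, and at 0.90, inside the plan's range, power does exceed 90%. Row 4-8, read by its own footnote, agrees with the sentence and may be its source. Figure 4-8 is not shown in the copy reviewed, so the method behind the row cannot be checked, and the 0.00 entries may be default values. The 0.75 in 15.6 also lies inside the appendix range, so the two rates do not strictly conflict.

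The second reply concerns weight. Section 15.6 ranks this test below estimation, and 15.12 says: "Population inferences will rely on point and interval estimates, and secondarily on two kinds of tests". The sample size of 1600 rests on availability, recruitment, time and cost as well as on precision and power. The reported interval will itself show any imprecision.

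The points about weight stand, and they limit the consequence. The first reply does not rescue the figure: an unconditional >90% is met at neither rate the plan expects, and row 4-8 repeats the error at 0.60 and 0.80. The reversed null label in that row is minor, since 15.6 and the text of 15.12 state the null correctly. The survey-timing conflict is a separate matter of outcome definition and plays no part in the 49% and 61%.

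**Conclusion.** The concern holds. The stated power is correct only for adherence rates above about 0.897; at the plan's two point assumptions it is overstated by roughly 30 to 40 percentage points or more. The result rests on two one-sided tests at 0.05 each, 800 analysed per subgroup and no covariate adjustment. The documents give no basis for quantifying the effect of adjustment. Missing adherence data, for which 15.12 makes no allowance here, or any nonzero true difference would lower power further. The primary Aim 2a output, estimated rates and their difference with confidence intervals, is not affected. This should be corrected before the equivalence result is reported.

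**What to change.** In 15.12, replace the sentence with wording such as: with 800 per subgroup, margin 0.05 and one-sided size 0.05 per test, power at zero difference is about 31%, 49%, 61% and 91% at adherence rates of 0.60, 0.75, 0.80 and 0.90; failure to show equivalence is inconclusive and will be interpreted from the confidence interval for P1 − P2.

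In row 4-8, enter not attainable at 0.60 and 0.80. At 0.90, enter about 0.01 for 80% power and below 0.005 for 90%. Label the null as non-equivalence, to match 15.6. It would also help to use one planning rate in 15.6 and the appendix.

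Separately, reconcile the 3-month post-treatment time point in 15.6 with its own heading and Table 4. The sponsor should define how T2 and T3 combine into fully versus not fully adherent, and then compute power at the rate expected under that definition.

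The cost is protocol wording and one appendix row. No patients are added; the stated power of a secondary test becomes less favourable.
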